**17.2 If applicable, provide a power analysis.**

*NOTE: This may not apply to certain types of studies, including chart/records reviews, survey studies, or observational studies. This question is asked to elicit whether the investigator has an adequate sample size to achieve the study objectives and justify a conclusion.*

**Response:**

**A minimum of 104 subjects will be enrolled in the study, with at least 26 participants per group. The study was powered to detect a difference in probing pocket depth (PPD) of 35% between groups, and a standard deviation (SD) of 0.5 for the distribution of 6 month changes. A sample size of 24 per group was estimated assuming approximately 80% power (alpha = 0.05). A minimum 26 subjects per group with an attrition rate of 10% will be enrolled in this study.**

**10-14-2021: We are continuing recruitment to greater than 100 participants in order to balance the numbers of participants per cell, to increase the size of the control group (no perio disease and no diabetes), and to increase the numbers with diabetes but no perio disease so that we have a more solid base on which to complete vigorous data analyses.**

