**Response:**

1. Supportive Periodontal Therapy (SPT) using Paroex® mouthrinse (0.12% chlorhexidine) and Soft-Picks leads to improved clinical status and change in oral microbiome greater than when Scaling and Root Planing (SRP) only is used.

2. There will be about 35% who will be “Poor Responders” (PRs) (those needing Rescue Therapy). The number of PRs in diabetics will be higher than in non-diabetics. Poor Responders will have different clinical and microbiome in characteristics than responders.

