**Primary Endpoints:**

1. **Change in Probing pocket depth (PPD) at the 6-month post-SRP completed at Baseline.**

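### The 80% power claim in section 17.2 cannot be derived from its stated inputs, because the 35% difference has no millimetre value and the sidedness, test and contrast are missing

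*Combined protocol and SAP*

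**What the plan says.** The only primary endpoint (section 2.1) is "Change in Probing pocket depth (PPD) at the 6-month post-SRP completed at Baseline". No expected mean change, in either treatment arm, is given there or anywhere else in the protocol.

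The power analysis (section 17.2) gives the effect and the variability as follows: "The study was powered to detect a difference in probing pocket depth (PPD) of 35% between groups, and a standard deviation (SD) of 0.5". That SD describes 6-month change, and no unit is stated. The result is: "A sample size of 24 per group was estimated assuming approximately 80% power (alpha = 0.05"). The number is then raised to a minimum of 26 per group, 104 in all, for 10% attrition.

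Three further places bear on how to read this:

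- Section 4.1 has four groups: A (diabetic, SRP+SPT), B (non-diabetic, SRP+SPT), C (diabetic, SRP) and D (non-diabetic, SRP). Section 17.2 does not say which of them the power refers to.
- Section 1.1 places the main goal in type 2 diabetes, which suggests A against C. Hypothesis 1 in section 1.2 says that SPT "leads to improved clinical status and change in oral microbiome greater than when Scaling and Root Planing (SRP) only is used", without restriction to diabetics, which suggests A+B against C+D.
- Sections 5.1 and 11.1 describe the 104 (26 per group in 5.1) as participants who complete with full data. Section 17.2 describes them as enrolled.

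**The concern.** Power for a comparison of two means depends on the difference divided by the SD, and the two must be on the same scale. Here one is a percentage and the other an absolute value of change. A reader who wants to reproduce 24 per group must supply the missing mean, and must also guess the sidedness, the test and the contrast. Different reasonable guesses give quite different answers.

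This is the trial's only power statement, and it concerns the sole primary endpoint. If the SPT comparison is not significant, the report will naturally say that the trial had about 80% power against a 35% difference. Nobody could tell from the protocol what size of effect had been made unlikely. The protocol also says the results will be used to plan a larger study, whose designers would inherit the same figure.

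**Working it through.** **Inputs from the documents:** SD of 6-month change 0.5; alpha 0.05; 24 per group; approximately 80% power; difference 35% (all section 17.2).

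**Assumptions, not in the documents:** the SD is in mm; the comparison is a two-sample t test with equal groups; each participant contributes one value.

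**Formula.** With n per group and difference Δ, the noncentrality is Δ / (SD × √(2/n)) on 2n − 2 degrees of freedom. Power is the probability that a noncentral t variable exceeds the critical value.

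**Step 1: try to reproduce the plan's figure.** This is not possible from the stated inputs, because Δ in mm is missing. The remaining steps bracket it.

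**Step 2: what 24 per group detects.** The standard error is 0.5 × √(2/24) = 0.144 mm. The normal approximation gives (1.960 + 0.842) × 0.144 = 0.404 mm for 80% power, two-sided. The exact t calculation gives 0.413 mm. At 26 per group it is 0.396 mm.

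**Step 3: read 35% as 0.35 mm.** The noncentrality at 24 per group is 0.35 / 0.144 = 2.42.

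| Comparison | n per arm | Two-sided power | One-sided power |
|---|---|---|---|
| Two single groups | 24 | 66% | 77% |
| Two single groups | 26 | 70% | 80% |
| SRP+SPT pooled against SRP | 48 | 92% | 96% |

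For two single groups, 80% power needs 34 per group two-sided (33 by the normal approximation) or 26 one-sided. The pooled row assumes the same SPT effect in diabetics and non-diabetics, and an SD of 0.5 mm within each.

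**Step 4: read 35% as relative to the SRP-alone change.** Then Δ = 0.35 × that change. The change below is assumed; n = 24 per group, two-sided.

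| Assumed SRP-alone change (mm) | Δ (mm) | Power |
|---|---|---|
| 0.6 | 0.21 | 30% |
| 0.8 | 0.28 | 48% |
| 1.0 | 0.35 | 66% |
| 1.2 | 0.42 | 81% |

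Eighty per cent is reached at 0.413 / 0.35 = 1.18 mm.

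**Step 5: attrition.** 26 × 0.9 = 23.4, and 24 / 0.9 = 26.7, which rounds up to 27. Allowing for 10% loss, 26 enrolled falls about one participant per group short of 24. If 26 is the number completing, as section 5.1 says, the step does not arise.

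**Step 6: adjusting for Baseline PPD.** If PPD has the same variance at Baseline and 6 months, with correlation r between them, adjusting change for Baseline multiplies its SD by √((1 + r)/2). For assumed r of 0.3, 0.5 and 0.7 the SD becomes 0.403, 0.433 and 0.461 mm. Two-sided power for 0.35 mm at 24 per group becomes 84%, 78% and 73%, against 66% unadjusted.

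**The case against.** The strongest reply is that nothing here shows a miscalculation. Section 17.2 says only approximately 80%. A relative reading with an SRP-alone change near 1.2 mm gives 81% two-sided. A one-sided 0.05 test at 0.35 mm needs 26 per group, close to the 24 stated. Pooling the two SPT groups against the two SRP groups gives 92%. All of this stands, and it limits the point to missing specification.

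The power paragraph also ends with a citation, listed in section 3.2 as a randomised trial in type 2 diabetic subjects with chronic periodontitis. The reference change and the SD may come from there. That cannot be checked from the protocol, and a citation does not tell the reader which value was used, for which contrast, or with which test.

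Finally, section 17.1 calls the study a pilot limited to descriptive analyses, and the October 2021 note in 17.2 extends recruitment beyond 100. This softens the consequence without removing it. Section 17.1 also lists formal comparisons, and 17.2 makes a formal power claim, which the later note leaves unchanged.

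Three stronger readings are tempting and should be resisted:

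- A reader might infer that true power is 66%. That figure needs three assumptions the protocol does not make: that 35% means 0.35 mm, that the test is two-sided, and that single groups are compared. Numerically it is the same as assuming a 1.0 mm SRP-alone change.
- A reader might infer that the trial has only two-thirds of the power claimed. Even on the 66% reading the ratio is 66/80, or 83%.
- A reader might notice that Hypothesis 2 also uses 35% ("There will be about 35% who will be" Poor Responders) and suspect that the number was carried across. Nothing in the documents connects the two quantities.

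**Conclusion.** The stated 80% at 24 per group cannot be derived from section 17.2, because a percentage difference is paired with an absolute SD and no reference mean, sidedness, test or primary contrast is given. It is an incomplete specification, and neither an arithmetic error nor inadequate power has been shown.

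The gap is material. With two single groups of 24 and a two-sided test, power runs from 30% to 81% as the assumed SRP-alone change goes from 0.6 to 1.2 mm. With the difference held at 0.35 mm, the choice of contrast alone moves two-sided power from 66% to 92%. What can be said from the protocol's own SD, alpha and sample size is a detectable difference of 0.41 mm at 80% power (0.40 mm at 26 per group), given that the SD is in mm, the test is a two-sided t test, and two single groups are compared.

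**What to change.** **1. Replace the power sentence in section 17.2.** State the primary contrast (A against C, or A+B against C+D), the difference in mm, the sidedness, the test and the evaluable number. If 35% is kept, give the SRP-alone mean change it refers to and its source. For an unadjusted two-sided t test, the text could read:

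- For A against C: *With 24 evaluable participants per group, an SD of 0.5 mm for 6-month PPD change and two-sided alpha 0.05 (two-sample t test), the trial has 80% power for a between-group difference of 0.41 mm.* With 26 evaluable per group the figure is 0.40 mm.
- For A+B against C+D: the same sentence with 48 per arm and 0.29 mm, adding that a common SPT effect in diabetics and non-diabetics is assumed.

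If the original calculation was one-sided, say so and give both figures.

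**2. Settle the evaluable number.** Reconcile 24 after attrition (17.2) with 26 completing per group (5.1), and use the same number in 5.1, 11.1 and 17.2.

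**3. As a separate change, name the primary analysis** as 6-month PPD change adjusted for Baseline PPD, base the power statement on that model, and state the correlation assumed. Baseline PPD is already measured (section 10.1), so no data collection is added.

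The cost is a few sentences in 17.1 and 17.2, aligned wording in 5.1 and 11.1, and no extra participants. The rewritten statement may look less favourable than the present one, depending on the contrast chosen.

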**Group A: Diabetic, Scaling & Root Planing (SRP) + Paroex® + Soft-Picks**

**Group B: Non-Diabetic, SRP + Paroex® + Soft-Picks**

**Group C: Diabetic, SRP**

**Group D: Non-Diabetic, SRP**

## 5.0 Local Number of Subjects

5.1 *Indicate the total number of subjects that will be enrolled or records that will be reviewed locally.*

Response: **104 with complete data; 26 per group**

5.2 *If applicable, indicate how many subjects you expect to screen to reach your target sample (i.e. your screen failure rate).*

Response: **250**

5.3 *Justify the feasibility of recruiting the proposed number of eligible subjects within the anticipated recruitment period. For example, how many potential subjects do you have access to? What percentage of those potential subjects do you need to recruit?*

Response: **We have a list of participants in previous studies that have given us permission to re-contact them about new studies. We also have a successful history of being able to make and surpass recruitment goals. Tactics such as word of mouth, flyers and posters, and ads have worked well in the past.**

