**BASELINE VISIT:**

- 1. Review medical and dental histories.**
- 2. Baseline Taste Test**
- 3. Oral Health Examination:**
  - a) Plaque Index (PI)**
  - b) Probing Pocket Depth (PPD)**
  - c) Bleeding on Probing (BOP)**
  - d) Gingival Index (GI)**
  - e) Clinical Attachment Level (CAL)**
- 4. Collect samples:**
  - a) Blood (FBS, HbA1c, Insulin, hs-CRP and microbiome testing, and for future testing of C-peptide, proinsulin, total GLP-1, PYY,**

DPP-IV, glucagon, LPS, soluble-TNF $\alpha$  RI and RII, MGO, TMAO, creatinine, and for future unknown testing.

- b) Subgingival plaque and saliva.
- c) Fecal, skin, and vaginal samples

3. Treatment: All participants will receive full mouth SRP within one month of the baseline visit.

4. Oral health instruction: All participants will receive oral hygiene instruction from the hygienist.

5. Participants will be randomized into one of the four groups.

6. Groups A and B will receive the product, Soft-Picks, and information on how to use them.

7. Make an appointment for 3 months after Baseline Visit.

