Prior to either analysis, the data will be pre-processed for error-correction to remove low quality reads. A BLAST search will assign sequences to known reference sequences using regularly updated databases. Analyses will be performed to group sequences into an OTU table using computational methods developed by members of our group. The OTU table provides a global view of the bacterial composition comprising the microbiome. The 2000-processor Dell P4 (64-bit) Linux cluster at UB's Center for Computational Research (CCR) can process the large quantity of data generated in this pilot project.

**Data Analysis:** Statistical procedures will be limited to descriptive analyses in this pilot study. Following the 16S rRNA sequencing and data reduction steps, we will describe the subgingival microbiome composition and relative abundance (OTU table). To begin to understand potential differences in the groups, univariate statistical analysis and descriptive statistics will be performed to identify oral bacteria associated with diabetes status and treatment group. Numerical, graphical (boxplots, scatterplots), and formal

**comparisons (Student's t-test, ANOVA, regression, or non-parametric equivalents for sparse bacteria) will be produced for visualization of results. Other analytic techniques will be utilized as well.**

**Descriptive statistics as well as univariate statistical analysis will be performed to identify oral bacteria associated with diabetes status and treatment group. Multivariable logistic regression will be conducted to control for other risk factors. Principal Component Analysis (PCA) or Hierarchical Cluster Analysis (HCA) also will be used to further understand potential associations with diabetes status and treatment group.**

**The analyses planned for this pilot study will provide preliminary data for preparation of a larger more definitive study.**

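### The sample size rests on the unadjusted SD of 6-month PPD change, and no analysis model or baseline-PPD covariate is specified for the randomised SPT-versus-SRP comparison

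*Combined protocol and SAP*

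**What the plan says.** Section 2.1 gives the primary endpoint as "Change in Probing pocket depth (PPD) at the 6-month post-SRP completed at Baseline".

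Section 17.2 contains the only quantitative plan for it. It states: "The study was powered to detect a difference in probing pocket depth (PPD) of 35% between groups", with "a standard deviation (SD) of 0.5 for the distribution of 6 month changes". It arrives at 24 per group for about 80% power at alpha 0.05, and then sets enrolment: "A minimum 26 subjects per group with an attrition rate of 10% will be enrolled in this study". It gives no baseline SD, no baseline-to-6-month correlation and no residual SD after adjustment.

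Section 10.1 includes PPD in the oral health examination at the baseline visit, listed ahead of treatment and randomisation. Randomisation is described without stratification by baseline severity.

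Section 17.1 confines the pilot's statistics to description and then lists t-tests, ANOVA, regression and non-parametric equivalents within the text on oral bacteria. Its one explicitly covariate-adjusted model is also there: "Multivariable logistic regression will be conducted to control for other risk factors". No model is named for PPD, and baseline PPD is not listed as a covariate in any section.

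**The concern.** A raw change score subtracts baseline with a fixed coefficient of 1, whereas ANCOVA estimates that coefficient. When the two visits have equal variance, ANCOVA is the more precise of the two for any correlation below 1. An arm that starts deeper by chance also tends to show a larger reduction through regression to the mean. With 24 to 26 per group and no stratification on severity, nothing in the design limits that imbalance.

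Naming a test of PPD change would not by itself settle this. An unadjusted test of change, the comparison whose SD enters 17.2, would still give up precision for which the data are already collected. Leaving the choice open also allows the adjusted or the unadjusted result to be chosen after both have been seen.

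**Working it through.** **Inputs from 17.2:** SD of 6-month change 0.5; 24 per group; power about 80%; alpha 0.05.

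**Assumptions, because the protocol is silent:** two-sided test; SD in mm; correlation ρ between baseline and 6-month PPD from 0.3 to 0.9; equal variances at the two visits (relaxed in step 3).

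**1. The plan's own figure.** The 35% difference has no base and no value in mm, so 24 per group cannot be derived from the stated inputs.
- Read as 0.35 mm, two-sided: n = 2 × (1.960 + 0.842)² × 0.5² / 0.35² = 32.04, so 33 per group. With 24 per group, power is 68% by the normal approximation and 66.1% by the noncentral t.
- Read as 0.35 mm, one-sided: 26 per group are needed, and 24 give 78% (normal approximation). This comes close, but needs two unstated assumptions.
- Working back from 24 per group and 80% power, two-sided: difference = 0.5 × (1.960 + 0.842) × √(2/24) = 0.404, or 0.413 by the noncentral t (standardised 0.826).

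Below, the stated 80% is taken as given, and the 0.35 mm reading is shown beside it.

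**2. Effect of baseline adjustment.** With common visit variance σ²:
- variance of change = 2σ²(1 − ρ)
- residual variance after adjustment = σ²(1 − ρ²)
- ratio = (1 + ρ)/2, so residual SD = 0.5 × √((1 + ρ)/2)

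Noncentral-t power with 24 per group and 2 × 24 − 3 = 45 degrees of freedom:

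| ρ | Variance ratio | Residual SD | Power, from 80% | Power at 0.35 mm, from 66.1% |
|---|---|---|---|---|
| 0.3 | 0.65 | 0.403 | 93.5% | 83.7% |
| 0.5 | 0.75 | 0.433 | 89.9% | 78.2% |
| 0.7 | 0.85 | 0.461 | 85.9% | 73.0% |
| 0.8 | 0.90 | 0.474 | 83.9% | 70.6% |
| 0.9 | 0.95 | 0.487 | 81.9% | 68.2% |

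A 10-point gain from 80% needs ρ of about 0.49.

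**3. Unequal variances.** If the 6-month SD is k times the baseline SD, the ratio is k²(1 − ρ²)/(1 + k² − 2kρ).
- k = 1.2, ρ = 0.8: 0.5184/0.52 = 0.997, so power is 80.1% and there is almost no gain.
- k = 0.6, ρ = 0.5: 0.27/0.76 = 0.355, so power is 99.7%.

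**4. Pooled contrast.** Section 17.2 says only that the difference is between groups. If A + B is compared with C + D (48 v 48), unadjusted power at 0.35 mm is already 92.4%. Adjustment at ρ = 0.7 takes it to 95.7%, a gain of about 3 points.

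**5. Chance imbalance.** With equal variances the slope of change on baseline is ρ − 1. At ρ = 0.5, a change SD of 0.5 implies a baseline SD of 0.5/√(2 × 0.5) = 0.5. The standard error of the baseline difference is then 0.5 × √(2/24) = 0.144 mm. An arm that starts one standard error deeper is expected to show (1 − 0.5) × 0.144 = 0.072 mm extra reduction with no treatment effect.

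**The case against.** The strongest reply is that the protocol does not commit to an unadjusted test. A reader might infer from 17.2 that the PPD comparison is planned on raw changes. But an SD of changes in a sample-size paragraph is a design input, and a change endpoint is compatible with baseline-adjusted ANCOVA. Section 17.1 also mentions regression and leaves room for other techniques, although in the microbiome text. This stands: the documents show a trial powered without adjustment and a PPD model left unspecified. The missing primary analysis is the more basic gap, and this point concerns what should fill it.

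The size of the gain can also be challenged. A reader might infer a gain of about 10 points, but that is the single case of ρ near 0.5, equal variances, 24 per group and a true 80% starting point. The protocol supplies neither ρ nor a baseline SD, and its 80% cannot be reproduced. The entry criteria in 6.1 set how many teeth must have a pocket of at least 5 mm. They do not give the spread of PPD, and the per-participant summary is undefined, so ρ cannot be inferred from them. Only a conditional range is supported.

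Finally, omitting the covariate does not bias a randomised comparison on average over randomisations. What is lost is precision, together with protection against the imbalance that happens to arise, in a study that calls itself a pilot. That is fair and limits the weight of the point. It does not remove the case for a change that needs no new data.

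**Conclusion.** The concern holds as an omission. The trial is powered on the unadjusted SD of 6-month change, no PPD model is specified, and baseline PPD is collected but not used as a covariate. For a single-stratum SPT-versus-SRP comparison (A v C or B v D), ANCOVA would raise power from 80% to between about 82% (ρ = 0.9) and 94% (ρ = 0.3), with 90% at ρ = 0.5. This rests on 24 per group, two-sided alpha 0.05, equal variances and the unverified 80%. With unequal variances the gain runs from almost nothing to nearly 20 points, and it is smaller if the arms are pooled across strata. The first aim in 1.1 concerns SPT in participants with diabetes, which makes A v C, at the per-group size that 17.2 powers, a natural reading. The protocol does not define the contrast.

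Two stronger readings are not supported. A reader might infer that adjustment removes baseline imbalance at no cost. It corrects only for imbalance in measured baseline PPD, under a linear model, and uses one degree of freedom. A reader might also carry the chance-imbalance argument over to the diabetic versus non-diabetic comparison. Diabetes status is not randomised, so a baseline difference there need not be chance, and adjusting for it changes the question. The change is worth making. Its absence does not invalidate the trial.

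**What to change.** In 17.1 and 17.2, state that the randomised SPT-versus-SRP comparison of 6-month PPD change will be a linear model (ANCOVA). It should use one PPD summary per participant, with terms for treatment and for that participant's baseline PPD (same sites, same summary). Add a diabetes-status term if the two strata are analysed together. Keep the unadjusted comparison of change as a sensitivity analysis. Use the same baseline adjustment for the secondary BOP, CAL, Gingival Index and Plaque Index changes.

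In 17.2, also state the contrast, the absolute difference in mm, the sidedness and the assumed baseline-to-6-month correlation, so that the power figure can be reproduced. Keep the chance-imbalance rationale to the randomised contrast.

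The cost is a few sentences and one degree of freedom for the baseline covariate (one more if the diabetes term is used). No new data, visits or participants are needed. The text should be fixed before any comparison by treatment is seen.

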## 4.0 Study Design

4.1 *Describe and explain the study design (e.g. case-control, cross-sectional, ethnographic, experimental, interventional, longitudinal, observational).*

Response: A single-center, single-blind, randomized controlled clinical trial:

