## 6.0 Inclusion and Exclusion Criteria

6.1 *Describe the criteria that define who will be **included** in your final study sample.*

*NOTE: This may be done in bullet point fashion.*

**Response: Inclusion Criteria:** To be in this study subjects must meet all of the following criteria:

- 1) Be able to understand the informed consent form and be willing and able to read and sign it.
- 2) At least 25 years of age.
- 3) Be able to understand and follow directions for study procedures.
- 4) At least 14 natural teeth, not counting third molars (“wisdom teeth”).
- 5) For moderate periodontal disease: At least four (4) teeth with at least one (1) site with  $\geq 5$  mm pocket depth (PD) and at least two (2) of the affected teeth with  $\geq 2$  mm alveolar bone loss as shown on radiographs. For Severe periodontal disease: At least eight (8) teeth with at least one (1) site with  $\geq 5$  mm pocket depth (PD) and at least two (2) of the affected teeth with  $\geq 2$  mm alveolar bone loss as shown on radiographs.

6.2 *Describe the criteria that define who will be **excluded** from your final study sample.*

*NOTE: This may be done in bullet point fashion.*

**Response: Exclusion Criteria:** Presence of the following criteria results in ineligibility for this study;

- 1) Presence of orthodontic appliances (“braces”).
- 2) An abnormal condition of lips, lining of the mouth, tongue, or gums (except for periodontal disease). If subject has a cold sore, canker sore, or injury in their mouth, they may return after the sore or injury heals.
- 3) Abscess of the gingiva caused by periodontal disease, or visible gross tooth decay
- 4) A broken tooth root or an abscessed tooth, per clinician’s judgement. Subject may be allowed to participate in the study after the condition is successfully treated or the study dentist reviews the condition and does not feel it will jeopardize the results of the study.
- 5) Periodontal treatment in the past 6 months.
6. Antibiotic therapy in the past three (3) months.

- 7) Have used cigarettes or other tobacco products in the past year.
- 8) Body mass index (BMI) is  $> 45$ .
- 9) Have regularly used non-steroidal anti-inflammatory drugs (such as  $\geq 325$  mg aspirin or ibuprofen) over the past 3 weeks.
- 10) Regularly using drugs that weaken the immune system (such as corticosteroids taken by mouth or injection, and cyclosporine).
- 11) Have participated in another clinical research study in the past 30 days.

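### The 10-14-2021 recruitment note in section 17.2 enlarges two groups without periodontal disease, which inclusion criterion 5 excludes and no section of the supplied documents defines

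*Combined protocol and SAP*

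**What the plan says.** **Recruitment.** Section 17.2 first sets the sample size: "A minimum of 104 subjects will be enrolled in the study, with at least 26 participants per group". The 10-14-2021 note follows in the same response. It continues recruitment beyond 100 for three purposes: to balance the cells, "to increase the size of the control group (no perio disease and no diabetes"), and "to increase the numbers with diabetes but no perio disease". It adds that this should give a firmer base for analysis, without saying which analysis. The note is part of the live text of a protocol dated March 02, 2022, not an amendment log.

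**Eligibility.** Section 6.1, which defines the final sample, states "To be in this study subjects must meet all of the following criteria". Criterion 5 has a moderate and a severe category and none below. The moderate category starts at "At least four (4) teeth with at least one (1) site with" a pocket of 5 mm or more, plus radiographic bone loss of 2 mm or more on two of the affected teeth.

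**Design and procedures.** Section 4.1 describes "A single-center, single-blind, randomized controlled clinical trial" with four groups, A to D, formed by diabetes status and by SRP with or without the supportive products. An example is "Group D: Non-Diabetic, SRP". Section 10.1 (Baseline Visit) gives SRP to all participants and randomises them among the four groups. Section 5.1 sets the number at "104 with complete data; 26 per group". Section 20.3, in contrast, refers to the study as observational.

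**Endpoint.** Section 2.1 makes the change in probing pocket depth (PPD) 6 months after SRP primary.

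**The concern.** A coordinator applying section 6.1 would screen out the very people whom the note asks staff to recruit. A coordinator following the note would enrol people who fail criterion 5, and section 10.1 as written would then have them randomised and given SRP.

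The four group labels do not mention periodontal status. The mismatch therefore comes from criterion 5 and not from the labels, and the labels alone would not reveal it.

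The eligibility rule, the baseline procedures and the set of people in the primary comparison all depend on which text governs. The note speaks of increasing the size of these groups, so some of these people may already be enrolled. The documents give neither their number nor their status. Balancing the existing cells, also mentioned in the note, is not at issue.

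**Working it through.** The question is mainly one of consistency, so the texts are set side by side first.

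| Question | 17.2 note | 6.1 | 4.1 and 10.1 | 20.3 |
|---|---|---|---|---|
| Can people without periodontal disease enter? | Yes, in two groups | No (criterion 5) | Not addressed; all are randomised and receive SRP | Not addressed |
| Is there a non-randomised part? | Suggested by the term control group, which names none of A to D | Not addressed | No; randomised trial only | Calls the study observational |

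**1. Is there a definition elsewhere?** The background (3.1) mentions comparing people with and without periodontal disease, but only as rationale. The main aim in 3.1 concerns people with diabetes and periodontal disease. The microbiology endpoint in 2.1 is change after SRP or SRP plus supportive therapy, which an untreated group could not supply. Section 17.1 analyses by diabetes status and treatment group; periodontal status is not a factor. No supplied section gives the two groups entry criteria, visits, a target number, an endpoint or a place in an analysis. The note also does not define absence of disease. Someone with deep sites on three teeth fails criterion 5 without necessarily being free of disease.

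**2. Who counts toward the minimums?** 4 × 26 = 104, so the two stated minimums agree. Sections 5.1, 11.1 and 17.2 do not repeat the criterion 5 restriction beside these numbers, but section 6.1 imposes it on the whole sample.

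**3. What if such people were randomised and analysed?** Let Δ be the mean difference in 6-month PPD change between SRP plus supportive therapy and SRP alone among people with periodontal disease, and p the share without disease in each arm. Assume PPD is a full-mouth mean and that treatment makes no difference in people without disease. Then

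observed difference = (1 − p) × Δ + p × 0 = (1 − p) × Δ.

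The documents give no p. For illustration, p = 5%, 10% and 25% leave 0.95Δ, 0.90Δ and 0.75Δ. If PPD is instead limited to deep sites, people without such sites give no value and this formula does not apply. If the people form a separate cohort, p = 0 and the difference is Δ.

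**4. Can this be turned into power?** Section 17.2 states 24 per group, a 35% difference, SD 0.5, about 80% power and alpha 0.05. It gives no mean to which the 35% applies and does not say whether the test is one- or two-sided. With n = 2 × (z₁ + z₂)² × SD² / Δ², and 35% read as 0.35 mm (an assumption):

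- two-sided: 2 × (1.960 + 0.842)² × 0.25 / 0.1225 = 32.0, or 33 when rounded up from the unrounded value;
- one-sided: 2 × (1.645 + 0.842)² × 0.25 / 0.1225 = 25.2, or 26.

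A two-sided n of 24 needs about 0.404 mm, which is 35% of a mean change of about 1.16 mm (0.404 / 0.35 = 1.15 to 1.16) that the plan does not state. The plan's own 24 can be neither confirmed nor refuted, so the starting point for a power loss is not fixed.

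**The case against.** The strongest reply is that criterion 5 already settles the matter. Section 6.1 defines the final sample, people without periodontal disease fail it, and so they cannot enter the 26 per group, the 104 or the PPD comparison. This stands. A reader might infer that nothing in the plan keeps them out; that is wrong, because section 6.1 does so on its face.

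The second reply is that the note plainly means a reference group for the microbiome work. The term control group fits none of A to D, the background motivates such a comparison, and section 20.3 speaks of an observational study. This reading is at least as plausible as randomisation, and under it the primary comparison is untouched. It does not remove the defect, because such a cohort would then be undocumented and sections 4.1 and 20.3 would still disagree on whether it exists.

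The third reply is that this is a pilot whose statistics section 17.1 limits to descriptive analysis, so loss of power matters little. That is fair, and the point does not rest on power. Eligibility rules apply to a pilot too, and a descriptive difference is diluted in the same way.

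Finally, the Manual of Procedures named in section 10.3 was not available and may define these groups. Even so, sections 6.1 and 17.2 conflict as written.

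**Conclusion.** The conflict is real and lies in current text. The note in 17.2, criterion 5 in 6.1 and the baseline procedures in 10.1 cannot all be followed, and the two groups without periodontal disease are undefined in the supplied documents. The plan needs correcting on that ground alone.

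A reader might go further and infer that such people have been randomised, count toward the minimums, or have weakened the primary comparison. The documents do not support this: they show neither randomisation nor counting. The effect on the 6-month PPD difference is nil if the groups are a separate cohort. It is a reduction roughly equal to their share if they are randomised and analysed, PPD is a full-mouth mean, and treatment makes no difference to their PPD change. No power figure should be attached. The share, the effect in mm, the PPD definition (full mouth or deep sites) and the comparison (within diabetes stratum or pooled) are all unstated.

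**What to change.** Reconcile the 17.2 note with sections 4.1, 6.1, 10.1 and 20.3 in one of three ways:

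- **(a)** correct the note, if its description of the groups is wrong;
- **(b)** end recruitment of people without periodontal disease, and state how many are enrolled and whether any were randomised;
- **(c)** define them in sections 4 and 6 as separate non-randomised reference cohorts with their own entry criteria and endpoint, not counted toward 26 per group or 104.

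In every case, add to section 17.1:

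> Only randomised participants who met inclusion criterion 5 at the screening eligibility examination (section 10.1, Screening Visit item 3) enter the A–D comparison of 6-month PPD change; the number of randomised participants not meeting it is reported by arm.

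The sentence names the screening examination because the baseline examination could otherwise be meant. Screening precedes randomisation, so an exclusion on that examination, applied alike in all arms, does not break the randomised comparison. Whether the SRP statement in section 10.1 applies to people without periodontal disease is for the investigators to reconcile.

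**Cost.** Option (a) is a wording change. Option (b) adds a count and a status statement. Option (c) also needs a visit schedule and a stated treatment status, and so an IRB amendment. Under any option, people without periodontal disease who are already enrolled do not count toward the minimums: k such people in a group of 26 leave 26 − k. The number of eligible participants per group may have to be reported as lower, or more recruited.
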